### 7.2. Participant Discontinuation/Withdrawal From the Study

A participant may withdraw from the study at any time at his/her own request. Reasons for discontinuation from the study include the following:

- Refused further study procedures;
- Lost to follow-up;
- Death;
- Study terminated by sponsor.

At the time of discontinuing from the study, if possible, an early discontinuation visit should be conducted. See the SoA for assessments to be collected at the time of study discontinuation and follow-up and for any further evaluations that need to be completed.

The early discontinuation visit applies only to participants who are enrolled/randomized and then are prematurely withdrawn from the study. Participants should be questioned regarding their reason for withdrawal.

If a participant withdraws from the study, he/she may request destruction of any remaining samples taken and not tested, and the investigator must document any such requests in the site study records and notify the sponsor accordingly.

If the participant withdraws from the study and also withdraws consent (see Section 7.2.1) for disclosure of future information, no further evaluations should be performed and no additional data should be collected. The sponsor may retain and continue to use any data collected before such withdrawal of consent.

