### 7.3. Lost to Follow Up

A participant will be considered lost to follow up if he or she repeatedly fails to return for scheduled visits and is unable to be contacted by the study site.

The following actions must be taken if a participant fails to be available for a required study visit:

- The site must attempt to contact the participant and reschedule the missed visit as soon as possible. Counsel the participant on the importance of maintaining the assigned visit schedule, and ascertain whether the participant wishes to and/or should continue in the study;
- Before a participant is deemed lost to follow up, the investigator or designee must make every effort to regain contact with the participant (where possible, 3 telephone calls and, if necessary, a certified letter to the participant's last known mailing address or local equivalent methods). These contact attempts should be documented in the participant's medical record;
- Should the participant continue to be unreachable, he/she will be considered to have withdrawn from the study.

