For the primary efficacy analysis, the mITT set will be used and will be the primary analysis. A secondary analysis of the primary efficacy endpoint will be performed and will use mITT1 and mITT2 analysis set. For all other efficacy analyses mITT, mITT1, and mITT2 sets will be used (3 sets of analyses). The PP analysis set will be used in the analyses of primary efficacy endpoint. The Safety Analysis Set will be used in the analyses of the safety data.

For efficacy related analysis (mITT, mITT1 and mITT2), if a participant enters/is randomized into the study multiple times, a sensitivity analysis based on IA and PCD efficacy data will be conducted on the primary endpoint and all sensitivity analysis regarding primary endpoint. The data associated with first randomization will be included in the above sensitivity analyses conducted.

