6. ANALYSES AND SUMMARIES

6.1. Primary Endpoint

6.1.1. Primary Endpoint/Estimand Analysis

6.1.1.1. Main Analysis

The primary endpoint is proportion of participants with COVID-19 related hospitalization or death from any cause through Day 28 in the mITT population. The cumulative proportion of participants hospitalized for the treatment of COVID-19 or death during the first 28 days of the study will be estimated for each treatment group using the Kaplan-Meier method to take account of losses to follow-up and summarized graphically for each treatment group.

The estimand is then the difference of the proportions in the 2 treatment groups and its 95% confidence interval will be presented, as well as, the associated two-sample proportion test. For the 95% CI, the corresponding estimate of the standard error is computed using Greenwood's formula (Kalbfleisch and Prentice; 1980). The Greenwood's formula to estimate the variance of the difference of proportions at Day 28 is $[Var(S_{PF}(28)) + Var(S_{Placebo}(28))]$. Instead of dealing with $S(t_i)$ we will use the log-log approach to CI. The 95% CI will be computed for the estimate of L(t) = log(-log(S(t))), the log hazard function.

$$Var(\hat{L}(t)) = Var[log(-log(\hat{S}(t)))]$$

The CI will be in right range when we transform back to $S(t) = \exp(-\exp(L(t)))$. Antilogging this confidence interval will give a 95% confidence interval for the difference itself.

The above primary analysis will be conducted for the planned interim analyses as well. Two-sided 95% CI (adjusted for the planned interim analyses) and associated p-value (two-sample proportion test) for the null hypothesis of no difference between treatment groups will be presented. Significance level will be determined using the O'Brien-Fleming approach at the interim analysis and the final analysis. The overall significance level is set at 5% (2 sided).

For participants who complete Day 28 efficacy assessment (Day 34 visit), they will be censored at their last visits. For participants who discontinue before Day 28 assessment or are lost to follow-up, they will be censored at the last known date in the study.

Participants will be analysed under the mAb stratum assigned at randomization/baseline.

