The proportion of participants with COVID-19 related hospitalization or death from any cause through Day 28 will be summarized graphically using Kaplan-Meier plots for each of the treatment groups, the analyses will be done using mITT, mITT1, and mITT2 populations.

The sensitivity analysis associated with primary endpoint will be conducted using the mITT2 population set. Four additional sensitivity analysis for the primary endpoint will be performed:

- a sensitivity analysis excluding all data from India sites for the mITT population;
- a sensitivity analysis excluding all participants from Site 1470 for the mITT, mITT1 and mITT2 populations;
- a sensitivity analysis excluding participants from the sentinel cohort of the study treated with active treatment (3 doses of 100 mg) for the mITT population;
- An additional sensitivity analysis for participants with missing data (i.e., participant who was without any COVID-19 related hospitalization or death of any cause but discontinued from study due to lost to follow up and their last observations are <28 days) will be performed for the mITT population. The sensitivity analysis will implement the following event imputation methodology for those with missing data for primary endpoint:
 - If the participant's last observed data is prior to Day 21, then impute as an event with event day as day of last observed data +1.
 - If the participant's last observed data is on or after Day 21, do not impute an event and participant remains censored at day of last observed data.

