6.1.1.2. Supplementary Analyses

Supplemental analyses will be performed to the primary efficacy endpoint. See below:

- 1. An analysis in the mITT analysis set of the primary endpoint where participants who received a therapeutic COVID-19 mAb treatment postbaseline will be considered as an event for the endpoint (in addition to COVID-19 related hospitalization and death due to any cause) with mAb treatment date as the time of event.
- 2. A logistic regression model will be fitted to the primary endpoint of hospitalization/death and will include treatment and region effect as independent variables. In addition the stratification variables specified in Section 3.5 will be added to the model analyses depending on the analysis population. Odds ratios, 95% CI and p-values will be summarized (p-values will be reported from main model likelihood ratio test). Additional analyses may be performed adjusting for baseline covariates (such as age, gender, etc.) as additive terms to the primary model, if necessary. For the primary endpoint, a model including main terms and interaction term for treatment and region will be fitted and p-value from the interaction term will be summarized.
- 3. A completers only analysis similar to the primary efficacy analysis will be conducted. Completers are mITT participants who have been in the study for at least 28 days, or any participant with COVID-19 related hospitalization or Death from any cause through Day 28.

4. An analysis associated with primary endpoint will be conducted using the perprotocol (PP) population set.

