9. APPENDICES

Appendix 1. Summary of Efficacy Analyses

Endpoint	Analysis Type	Population	Data Inclusion and Rules for Handling Intercurrent Events and Missing Data	Analysis Model
Proportion of participants with COVID-19 related hospitalization or death from any cause through Day 28.	Primary Efficacy analysis	mITT	All data collected will be included regardless of intercurrent events. Kaplan- Meier method to take account of losses to follow-up.	Kaplan-Meier method
Proportion of participants with COVID-19 related hospitalization or death from any cause through Day 28.	Sensitivity analysis for primary endpoint	mITT2	All data collected will be included regardless of intercurrent events. Kaplan-Meier method to take account of losses to follow-up.	Kaplan-Meier
Proportion of participants with COVID-19 related hospitalization or death from any cause through Day 28.	Sensitivity analysis for primary analysis	mITT	Analysis excluding all data from India sites and participants from Site 1470.	Kaplan-Meier method
Proportion of participants with COVID-19 related hospitalization or death from any cause through Day 28.	Sensitivity analysis for primary analysis	mITT	Analysis excluding all participants from Site 1470.	Kaplan-Meier method
Proportion of participants with COVID-19 related hospitalization or death from any cause through Day 28.	Sensitivity analysis for primary analysis	mITT	Analysis excluding participants from the sentinel cohort of the study treated with active treatment (3 doses of 100 mg).	Kaplan-Meier method
Proportion of participants with COVID-19 related hospitalization or death from any cause through Day 28.	Sensitivity analysis for primary analysis	mITT	If the participant's last observed data is prior to Day 21, then impute as an event with event day as day of last observed data +1. If the participant's last observed data is on or after Day 21, do not impute an event and participant remains censored at day of last observed data	Kaplan-Meier method
Proportion of participants with COVID-19 related	Supplemental analysis for primary analysis	mITT	All data collected will be included regardless of intercurrent events.	logistic regression model

Endpoint	Analysis Type	Population	Data Inclusion and Rules for Handling Intercurrent Events and Missing Data	Analysis Model
hospitalization or death from any cause through Day 28.			Use stratification variables as in Section 3.5.	

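### The only primary-endpoint analysis that imputes events for dropouts covers loss to follow-up alone, and Appendix 1 omits that restriction; a minor second point is that the sentinel exclusion removes active-arm participants only

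*SAP*

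**What the plan says.** SAP 6.1.1.1 sets the primary censoring rule, with the last date of known participation as the censoring date, for two groups named separately: "For participants who discontinue before Day 28 assessment or are lost to follow-up, they will be censored".

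The missing-data sensitivity analysis in the same section, run in mITT, defines missing data by a closed i.e. clause: participants without the endpoint who "discontinued from study due to lost to follow up and their last observations are <28 days". Within that group, last data before Day 21 leads to an imputed event on the next day, and last data on or after Day 21 leaves the participant censored.

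Both Appendix 1 rows for this analysis (all mITT data, and first randomization only) carry the rule alone: if the "last observed data is prior to Day 21, then impute as an event with event day as day of last observed data +1". Neither row mentions loss to follow-up.

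Protocol 7.2 lists "Refused further study procedures" as a reason for leaving the study, separate from loss to follow-up, death and "Study terminated by sponsor". Protocol 7.3, on loss to follow-up, ends: "Should the participant continue to be unreachable, he/she will be considered to have withdrawn from the study".

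The sentinel sensitivity analysis (SAP 6.1.1.1 and two Appendix 1 rows) removes sentinel participants given active treatment, described as three doses of 100 mg. Protocol 6.1.1 says that some sentinel participants may receive 100 mg tablets or the matching placebo, taken as three tablets every 12 hours.

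**The concern.** A check on a censoring rule should vary that rule for the participants to whom it applies. Here it does so for one recorded reason only. An event-free participant who refuses follow-up on Day 6, say, is censored in the primary analysis and again in the check, so for that group nothing is tested.

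The group matters a little more under the current SAP than under the protocol. SAP Section 4 no longer requires a postbaseline visit for mITT, so participants who leave soon after the first dose are now in the primary set and are censored almost at once.

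The SAP also gives two definitions. A programmer working from 6.1.1.1 imputes for losses to follow-up only. One working from Appendix 1 alone would impute for every early discontinuation. Because SAP Section 4 plans a first-randomization analysis "a sensitivity analysis based on IA and PCD efficacy data will be conducted on the primary endpoint and all sensitivity analysis regarding primary endpoint", the unrestricted wording could also reach participants who are simply still in follow-up at the interim data cut.

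The sentinel check makes an exclusion that depends on treatment arm, which the primary analysis does not do.

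**Working it through.** **Does another analysis fill the gap?** SAP 6.1.1.2 lists four supplementary analyses.
- The analysis that counts postbaseline mAb treatment as an event does not count dropout.
- The completers analysis drops event-free early leavers: "Completers are mITT participants who have been in the study for at least 28 days", plus anyone with an event.
- The logistic regression has no rule of its own for dropouts. SAP 5.3 has a general carry-forward statement for efficacy data that are not time-to-event, but its only specific rule concerns symptoms.
- The per-protocol analysis changes the population, not the handling of dropouts.

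None imputes events for refusals or withdrawals.

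**Design figures.** The inputs are 7% vs 3.5%, 90% power, two-sided 5% and 1:1 allocation (SAP 2.2 and 2.3). The standard two-proportion formula gives 852 per arm, 1704 in total, 0.8% below the stated 1717. The total is 1717/(0.80 × 0.75 × 0.95) = 3012, against about 3000 stated. Below, n = 1717/2 = 858.5 per arm.

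**Illustration for (a).** The only dropout figure in the documents is 5%. Let d be dropout in an arm, e the share of it before Day 21, f the share of that imputed, and p the design event rate. Dropouts who are not imputed are treated as removed, which approximates early censoring.
- Event proportion = (d·e·f + (1 − d)·p) / (1 − d + d·e·f)
- Effective n = 858.5 × (1 − d + d·e·f)
- Test: unpooled z

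Equal dropout, e = 1:

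| d | f | Difference (points) | p |
|---|---|---|---|
| 5% | 0.25 | 3.45 | 0.004 |
| 5% | 0.50 | 3.41 | 0.009 |
| 5% | 0.75 | 3.37 | 0.014 |
| 5% | 1 | 3.33 | 0.021 |
| 2% | 0.25 | 3.48 | 0.002 |
| 2% | 1 | 3.43 | 0.006 |

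Unequal dropout, 5.5% active and 4.5% placebo, e = 1:
- Narrow set (f = 0.5). Active: (0.0275 + 0.945 × 0.035)/0.9725 = 6.23%. Placebo: (0.0225 + 0.955 × 0.07)/0.9775 = 9.14%. Difference 2.91 points, z = 2.24, p = 0.025.
- Broad set (f = 1). Active: 0.055 + 0.033075 = 8.81%. Placebo: 0.045 + 0.06685 = 11.19%. Difference 2.38 points, z = 1.64, p = 0.10.

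Solving for the excess of active over placebo dropout at which p = 0.05, with f = 0.5 for the narrow set and f = 1 for the broad set, gives the range in which the two sets fall on opposite sides of 0.05:

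| Mean dropout | Share before Day 21 | Excess on active (points) | Participants (× 858.5) |
|---|---|---|---|
| 5% | all | 0.52 to 1.73 | 4.5 to 14.8 |
| 5% | 75% | 0.91 to 2.56 | 7.8 to 22.0 |
| 5% | half | 1.73 to 4.23 | 14.8 to 36.4 |
| 2% | all | 1.05 to 2.42 | 9.0 to 20.8 |

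If placebo dropout is the higher (4% active, 6% placebo, e = 1), the broad set strengthens the result: z = 3.62, p = 0.0003.

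**Illustration for (b).** About 60 sentinel participants at 1:1 give about 30 on active. With the whole-trial expected shares, 30 × 0.75 × 0.80 = 18 are in mITT. Up to about 30 is possible. Compared with a symmetric exclusion, the placebo-minus-active difference moves by m/(858.5 − m) × (r − 0.07), where m is the number of retained placebo participants and r their event rate, assumed to lie between 0% and 19%.
- m = 18: −0.15 to +0.26 points
- m = 30: −0.25 to +0.43 points
- Standard error of the difference: √(0.035 × 0.965/858.5 + 0.07 × 0.93/858.5) = 1.07 points

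**The case against.** **A narrow set can be defended.** Someone who refuses can be asked why. An early discontinuation visit is planned where possible, and the schedule of activities includes vital status and adverse event checks at early termination. An unreachable participant has none of this. Counting every withdrawal before Day 21 as a hospitalization or death, against design rates of 3.5% and 7%, is severe. This stands as a reason not to replace the current analysis. It does not supply the missing check, because status after refusal is still unknown and the SAP gives no rationale for the limit.

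**The current rule may be agreed with the regulator.** The SAP version history (V1.3) records a sensitivity analysis requested by FDA without naming it. If it is this one, substitution would be wrong. That also supports adding rather than replacing.

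**Appendix 1 is only a summary.** This stands in part. A reader might infer that three conditions are missing there. The event-free and before-Day-28 conditions are largely implied, since nobody who already has an event is given one and staying censored presupposes no event. The restriction to loss to follow-up is the one material omission.

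**Protocol 7.3 may not make the reason codes unreliable.** A reader might infer that true losses will be recorded as withdrawals. The documents do not show this. Protocol 7.2 lists loss to follow-up as its own reason, 8.3.3 points to 7.3 for its definition, and the closing sentence of 7.3 can describe study status. What remains is that the SAP should say which recorded reasons count.

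**Conclusion.** The gap in the sensitivity analysis and the mismatch with Appendix 1 are real and worth correcting. They concern a robustness check only. No decision rule attaches to it, and the primary estimate, test, alpha and sample size do not depend on it.

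A reader might infer that the restriction hides a fragile result. The documents do not support that. At design rates, equal dropout leaves the reading unchanged at every imputed share. A change needs several assumptions together: mostly early dropout, a substantial share not due to loss to follow-up, and more dropout on active. The range of 0.5 to 1.7 points belongs to one case (5% mean dropout, all before Day 21, half lost to follow-up). Later or rarer dropout needs a larger imbalance, up to 1.7 to 4.2 points when half is early. All of this is illustrative, since timing, reason and arm split are not given.

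The sentinel point is minor. The shift is at most 0.43 points in size under the assumptions used, below half of one standard error. The figure of 18 is an expected count, not a ceiling.

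**What to change.** (a) Keep the current analysis. Beside it in SAP 6.1.1.1, add the same Day 21 rule for every event-free mITT participant who discontinued the study with last observation before Day 28, whatever the recorded reason. Exclude from imputation those still in follow-up at a data cut and those whose participation ended because the sponsor terminated the study. State which recorded reasons count as loss to follow-up. Give both versions matching definitions in the two Appendix 1 missing-data settings, or cross-refer to 6.1.1.1. If the data are already unblinded, label the addition as made after unblinding.

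(b) In 6.1.1.1 and both Appendix 1 sentinel rows, exclude from both arms the participants dispensed the 100 mg presentation or its matching placebo, or else the whole sentinel cohort. The SAP description in doses and the protocol description in tablets every 12 hours must be reconciled.

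The cost is SAP wording, one added analysis and one re-run. The broader set may look less favourable, and the symmetric exclusion of the 100 mg presentation removes about 18, possibly up to about 30, further placebo participants from that check.

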6.1.1.2. Supplementary Analyses

Supplemental analyses will be performed to the primary efficacy endpoint. See below:

- 1. An analysis in the mITT analysis set of the primary endpoint where participants who received a therapeutic COVID-19 mAb treatment postbaseline will be considered as an event for the endpoint (in addition to COVID-19 related hospitalization and death due to any cause) with mAb treatment date as the time of event.
- 2. A logistic regression model will be fitted to the primary endpoint of hospitalization/death and will include treatment and region effect as independent variables. In addition the stratification variables specified in Section 3.5 will be added to the model analyses depending on the analysis population. Odds ratios, 95% CI and p-values will be summarized (p-values will be reported from main model likelihood ratio test). Additional analyses may be performed adjusting for baseline covariates (such as age, gender, etc.) as additive terms to the primary model, if necessary. For the primary endpoint, a model including main terms and interaction term for treatment and region will be fitted and p-value from the interaction term will be summarized.
- 3. A completers only analysis similar to the primary efficacy analysis will be conducted. Completers are mITT participants who have been in the study for at least 28 days, or any participant with COVID-19 related hospitalization or Death from any cause through Day 28.

4. An analysis associated with primary endpoint will be conducted using the perprotocol (PP) population set.

6.2. Secondary Endpoint(s)

6.2.1. Proportion of Participants with COVID-19 Related Hospitalization or Death due to All Cause through Day 28 in mITT1 Analysis Set

The proportion of participants with COVID-19 related hospitalization or death due to any cause through Day 28 in the mITT1 analysis set will be similar to the primary endpoint analysis.

6.2.2. Incidence of Treatment Emergent Adverse Events (TEAEs)

The incidence of TEAEs will be summarized by treatment group, by system organ class (SOC) and preferred term (PT) using the SAS population.

6.2.3. Incidence of SAEs and AEs Leading to Discontinuations

The incidence of SAEs and AEs leading to discontinuation will be summarized by treatment group using the SAS population.

6.2.4. Time (days) to Sustained Alleviation and Time to Resolution of Targeted COVID-19 Sign/Symptoms through Day 28

The time (days) to sustained alleviation and time to resolution will be defined for all targeted COVID-19 associated symptoms based on self-assessment.

Sustained alleviation of all targeted COVID-19 signs/symptoms is defined as the event occurring on the first of 4 consecutive days when all symptoms scored as moderate or severe at study entry are scored as mild or absent AND all symptoms scored mild or absent at study entry are scored as absent. The first day of the 4 consecutive-day period will be considered the First Event Date.

Sustained resolution is defined as when all targeted symptoms are scored as absent for 4 consecutive days. The first day of the 4 consecutive-day period will be considered the First Event Date.

For symptoms with no reported severity in baseline, the symptom will have to be absent in order to be counted as sustained alleviated/resolved (missing severity at baseline will be treated as mild).

Day 25 is the last possible day the symptom alleviation and resolution endpoints can be achieved (definition includes data from the subsequent three days) and Day 28 is the last day participants report their daily signs and symptoms.

The time to sustained symptom alleviation/resolution for the purpose of this study is defined as:

PFIZER CONFIDENTIAL
Page 23

- For a participant with sustained symptom alleviation/resolution (event), time to event will be calculated as (First Event Date) (First Dose Date) +1.
- For a participant that either completes Day 28 of the study or discontinues from the study before Day 28 without sustained symptom alleviation/resolution (censored), censoring date will be at the last date on which symptom alleviation/resolution is assessed, and time will be calculated as (Censoring Date) (First Dose Date) +1 or Day 25 whichever occurs first.

The decision to require 4 consecutive days with all targeted symptoms absent was based on exploratory analyses of data from the ACTIV-2/A5401 study, which suggested that this choice (rather than requiring fewer consecutive days) better captured sustained symptom resolution with low probability of subsequent relapse.

Participants who are hospitalized for the treatment of COVID-19 or death from any cause during the 28-day period will be classified as not achieving sustained symptom alleviation/resolution and will be censored at day 25.

Cox proportional hazard model analyses will be used for time to sustained symptom alleviation/resolution. Cox proportional hazard model will include treatment and region effect as independent variables. In addition, the stratification variables specified in Section 3.5 will be added to the model analyses depending of the analysis population.

Time to sustained symptom alleviation/resolution will be summarized graphically using Kaplan-Meier plots for each of the treatment groups, the analyses will be done using the mITT population only.

In the mITT populations, the analysis will be repeated in subgroups based on baseline serology status (positive, negative), by baseline viral load ($<10^4$ copies/mL, $\ge 10^4$ copies/mL), and ($<10^7$ copies/mL, $\ge 10^7$ copies/mL).

6.2.5. Proportion of Participants with Severe Signs/Symptoms Attributed to COVID-19 through Day 28

Participants will record a daily severity rating of their symptom severity over the past 24 hours based on a 4-point scale in which 0 is reported if no symptoms were present; 1 if mild; 2 if moderate; and 3 if severe.

Vomiting and diarrhea will each be rated on a 4-point frequency scale where 0 is reported for no occurrence, 1 for 1 to 2 times, 2 for 3 to 4 times, and 3 for 5 or greater. Sense of smell and sense of taste will each be rated on a 3-point Likert scale where 0 is reported if the sense of smell/taste was the same as usual, 1 if the sense of smell/taste was less than usual, and 2 for no sense of smell/taste.

The proportion of participants with any severe targeted signs/symptoms attributed to COVID-19 through Day 28 will be summarized by treatment group. A participant with severe score for any targeted symptoms post-baseline will be counted as severe. Proportions for each targeted signs and symptom with severe category only will be plotted over time through Day 28. Additionally, the proportion of participants reporting the presence of each targeted sign and symptom that is mild, moderate or severe categories will also be presented. In addition, to understand the severity of signs/symptoms attributed to COVId-19, the following analysis will be performed:

- 1. Proportion of participants with any severe targeted signs/symptoms attributed to COVID-19 at DAY 1 (baseline).
- 2. Proportion of participants with any severe targeted signs/symptoms attributed to COVID-19 Day 2 to Day 6 (during treatment).
- 3. Proportion of participants with any severe targeted signs/symptoms attributed to COVID-19 Day 7 to Day 28 (post treatment).

Treatment comparison between the group will be presented as odds ratio and 95% CI using logistic regression with a similar analysis model as specified in Section 6.1.1.2. The analyses will be done using mITT, mITT1, and mITT2 populations.

In the mITT population, the analysis will be repeated in subgroups based on baseline serology status (positive, negative), by baseline viral load ($<10^4$ copies/mL, $\ge10^4$ copies/mL) and ($<10^7$ copies/mL, $\ge10^7$ copies/mL).

An additional follow-up analysis for signs/symptoms data will be conducted at Week 12 and Week 24 for all signs/symptoms (not just targeted signs/symptoms, See Appendix 5). The Week 12 and Week 24 signs/symptoms data is collected from a long-term FU telemedicine interview performed by the site to participant and collected in CRF (diary data is not colected after Day 34).

The observed proportion of participants with any mild, moderate, and severe of all signs/symptoms attributed to COVID-19 at Week 12 and Week 24 will be summarized by treatment group and overall. Observed proportion of participants reporting the presence of each sign and symptom that is mild, moderate, or severe categories will also be summarized by treatment group and overall.

The analyses will be done using mITT, mITT1, and mITT2 populations.

6.2.6. Duration of Each Targeted COVID-19 Sign/Symptom through Day 28

Duration of each targeted COVID -19 signs/symptoms is defined as (First Date when the symptom alleviated/resolved) – (First Dose Date) +1 for each participant with baseline severity of mild, moderate or severe.

PFIZER CONFIDENTIAL
Page 25

Duration of each targeted COVID-19 sign/symptom with a mild or worse severity will be summarized for each group within mITT, mITT1, and mITT2 populations.

For duration of each targeted COVID19 sign/symptom, a Kaplan-Meier analysis providing the median and quartiles will be provided for each treatment group for mITT population set. Two additional figures (Number of Participants and Median Time to Sustained Alleviation of Each Targeted Sign/Symptom by Treatment Group [mITT) will be included for the endpoint of Duration of Each Targeted COVID-19 Sign/Symptom.

6.2.7. Progression to a Worsening Status in 1 or More Self-reported COVID-19 Associated Symptoms through Day 28

Participants will record a daily severity rating of their symptom severity over the past 24 hours based on a 4-point scale in which 0 is reported if no symptoms were present; 1 if mild; 2 if moderate; and 3 if severe. Vomiting and diarrhea will each be rated on a 4-point frequency scale where 0 is reported for no occurrence, 1(mild) for 1 to 2 times, 2 (moderate) for 3 to 4 times, and 3 (severe) for 5 or greater.

Progression to a worsening status for any targeted symptom will be derived programmatically based upon increasing severity (ie, the first time any targeted symptoms worsen after treatment relative to baseline):

Progression to worsening (Yes/No)	
Increasing severity	Yes
Not increasing severity	No

The proportion of participants with progression (increasing severity for any targeted symptom) will be summarized by treatment group. Treatment comparison between groups will be presented as odds ratios with 95% confidence intervals and P-value based on logistic regression model as specified in Section 6.1.1.2. The analyses will be done using mITT, mITT1, and mITT2 population. Missing severity at baseline will be treated as mild.

6.2.8. Proportion of Participants with a Resting Peripheral Oxygen Saturation ≥95% at Days 1 and 5

The oxygen saturation level will be measured for each participant. A resting peripheral oxygen saturation will be derived programmatically based on the following table:

Oxygen saturation (Yes/No)	
≥95%	Yes
<95%	No

PFIZER CONFIDENTIAI	
Page 26	

The count and proportion of participants with a resting peripheral oxygen saturation $\geq 95\%$ will be summarized by treatment group and by visits (Days 1 and 5). A cross table will be presented for both Day1 and Day 5, ie, for each proportion presented at Day 1, both proportions at Day 5 will be summarized. Treatment comparison between group for the odds ratio (baseline (Day 1) $\geq 95\%$ vs < 95) of comparing oxygen saturation $\geq 95\%$ at Day 5 will be analyzed with a Breslow-Day test for homogeneity of the odds ratios. The analyses will be done using mITT, mITT1, and mITT2 populations. Missing data at Day 1 or Day 5 will be excluded from the analysis.

6.2.9. Proportion of Participants with Death (all-cause) Through Week 24

The proportion of participants with death (all-cause) through Week 24 will be summarized by treatment group. Treatment comparison between the group will be presented as odds ratio and its 95% CI using logistic regression with a similar analysis model as specified in Section 6.1.1.2. The analyses will be done using mITT, mITT1, and mITT2 populations.

If zero counts are observed in either treatment group, the Fishers Exact test will be performed (instead of logistic regression) and pvalue provided.

As mortality is the most important of the efficacy at Week 24, this pertains specifically to that endpoint. If the impact s minimal (defined below), then no sensitivity analysis is required.

